**Job Notes:** 

This is the second revision (Version 3.0) of the Statistical Analysis Plan for this study. This version of the Statistical Analysis Plan is based on Version 10.0 of the study protocol.

Status: Approved, Version: 3.0 Page 2 of 18 Approved Date: 22 Nov 2022

Document ID: V-CLN-0002688

#### **Executive Summary:**

#### Key Objectives:

The primary objective of this study is to report the rate of post-surgical intraocular inflammation (based upon a specified case definition) reported within a 180-day post-surgical period following attempted implantation of an ACRYSOF IQ ReSTOR Toric IOL or ACRYSOF IQ ReSTOR IOL in the US.

#### 1 STUDY OBJECTIVES AND DESIGN

# 1.1 Study Objectives

The primary objective is to report the rate of post-surgical intraocular inflammation (based upon a specified case definition) reported within a 180-day post-surgical period following attempted implantation of an ACRYSOF IQ RESTOR Toric IOL or ACRYSOF IQ RESTOR IOL in the US.

# 1.2 Study Description

This is a prospective, multi-center, active surveillance post-approval study designed to estimate the incidence of post-surgical intraocular inflammation (based upon a specific case definition) in approximately 3,300 eyes that have been implanted with an ACRYSOF IQ RESTOR Toric IOL or ACRYSOF IQ RESTOR multifocal IOL in the US (Cohort 2) for up to 180 days. Active surveillance will be conducted through systematic collection, analysis, and interpretation of all reported cases of post-surgical intraocular inflammation over 4 visits ranging from 1 to 180 days post implantation of the ACRYSOF IQ RESTOR Toric or ACRYSOF IQ RESTOR IOL. The ACRYSOF IQ RESTOR Toric IOL and ACRYSOF IQ

RESTOR IOL are commercially available in the United States. This study will include adults (≥ 22 years of age) with preoperative cataract in the study eye(s). Potential subjects will be screened for enrollment into the study. Those qualifying will be considered enrolled in the study at the time the informed consent form is signed and attend a total of up to 11 scheduled visits. The subject will be considered exposed to treatment at the time of surgery when the investigational product touches the eye.

The study includes two groups of subjects (Cohort 1 and Cohort 2).

Cohort 1: Subjects implanted from November 2018 through July 2020 with ACRYSOF IQ RESTOR +3.0 D Multifocal Toric IOL (Models SND1T3, SND1T4, SND1T5 or SND1T6) or an ACRYSOF IQ RESTOR +2.5 D Multifocal Toric IOLs (Models SV25T3, SV25T4, SV25T5, and SV25T6) in at least one eye.

Note: At time of Protocol Amendment 7, Cohort 1 enrollment is complete.

Cohort 2: Subjects implanted after July 2020 with ACRYSOF IQ RESTOR +3.0 D Multifocal Toric IOL (Models SND1T3, SND1T4, SND1T5 or SND1T6) or an ACRYSOF IQ RESTOR +2.5 D IOL (Model SV25T0) in at least one eye.

Note: This Cohort will include subjects enrolled under Amendment 7 and later.

An overview of the study design is depicted in Figure 7-1 of the protocol, and the schedule of visits is presented in Table 12-1.

#### 1.3 Randomization

Not applicable.

# 1.4 Masking

Not applicable.

# 1.5 Interim Analysis

Interim reports pertaining to the progress of the post-approval study will be submitted to the FDA for review every six months up to the first two years, or as requested, starting from the date of FDA approval of the ReSTOR +3.0 D Toric intraocular lens, and will continue to be submitted annually thereafter until study completion.

For each interim report, the number of eyes enrolled, the number of eyes with an attempted implantation and the number of eyes with successful implantation of the ACRYSOF IQ RESTOR study IOLs will be reported. In addition, the rates for post-surgical intraocular inflammation, Toxic Anterior Segment Syndrome (TASS), acute postoperative endophthalmitis, chronic postoperative endophthalmitis, and uncategorized cases of post-surgical intraocular inflammation (based upon the specified case definition) will be reported, and a listing of all such events will be provided. A listing of all ocular serious adverse events will also be provided.

#### 2 ANALYSIS SETS

Subject evaluability will be determined prior to locking the database for each cohort, accordingly, based upon the Deviation and Evaluability Plan (DEP).

In the case that the integrity, quality, and accuracy of the data are suspect for a site or parameter an evaluation of the findings will be done and appropriate statistical analysis conducted to mitigate bias in the results will be determined, including possible exclusion of site or parameter from the analysis.

# 2.1 Efficacy Analysis Sets

Not applicable.

# 2.2 Safety Analysis Set

The safety set includes all eyes with attempted test article implantation (successful or aborted after contact with the eye). The safety set will be the primary analysis set for all safety analyses. Modified safety set includes all eyes with successful test article implantation. The modified safety set will be used for a sensitivity analysis of the primary safety endpoint.

Second eye surgery within 6 months of the occurrence of first cataract surgery will be included in the primary analysis. Second eye surgeries after 6 months of the first surgery are also included. If both eyes of a subject are enrolled in this study, full follow-up information from both eyes will be used in the primary analysis. The above definition applies to both Cohort 1 and Cohort 2.

Unless otherwise specified, analyses described below will be reported only for Cohort 2.

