# 5.3.1 Post-Surgical Intraocular Inflammation

For the primary safety endpoint, the rate (per 1,000 IOL implants) of post-surgical intraocular inflammation (based upon the specified case definition) reported within a 180-day post-surgical period following attempted implantation of study IOLs (Cohort 2) in the United States will be estimated along with the exact two-sided 95% confidence interval. The event rate (per 1,000 IOL implants) is calculated as:

Total # of reported events/Total # of attempted implants x 1,000

An eye with multiple reports of inflammation is only counted once toward the total of the inflammation cases and the one related to device will take precedence. The inflammations related to the device will also be summarized. Event rates will be presented by first eye, second eye, and overall eyes, respectively. A subgroup analysis on the primary safety endpoint will be performed by age groups (22-64 years vs. 65 years or older). If both eyes of a subject are enrolled in this study, full follow-up information for both eyes will be used in the primary analysis.

As sensitivity analyses, cumulative event rates of post-surgical intraocular inflammation (based upon the specified case definition) at 180 days will be provided using Kaplan-Meier estimator for first eyes, second eyes, and overall eyes. The corresponding two-sided 95%

confidence interval of the rates will also be provided. Graphical presentations of the Kaplan-Meier post-surgical intraocular inflammation curves for overall eyes will be included. Kaplan-Meier estimators will be calculated using two different censoring rules as follows:

- 1. Full follow-up information for both eyes is used. If an eye does not have inflammation, then follow-up is censored at the time (days) from each surgery to the last known date in the study for each eye;
- 2. If a subject has a second cataract surgery within 180 days of the occurrence of the first cataract surgery, the follow-up for the first eye will be censored at the time of second surgery, in the case of no inflammation before the second surgery, for calculating rates for first eyes.

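### Does the overlap between the Cohort 1 and Cohort 2 implant dates leave the primary denominator undefined?

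*SAP*

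**What the plan says.** Section 1.2 states that the study has two groups of subjects and describes each by implant period:

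- Cohort 1: "Subjects implanted from November 2018 through July 2020 with ACRYSOF IQ RESTOR +3.0 D Multifocal Toric IOL", or a +2.5 D toric model.
- Cohort 2: "Subjects implanted after July 2020 with ACRYSOF IQ RESTOR +3.0 D Multifocal Toric IOL", or the non-toric +2.5 D model SV25T0.

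In both, one eye with a listed lens suffices. Models SND1T3 to SND1T6 are in both lists.

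A Note follows each description. The one under Cohort 1 records that its enrolment had finished by Amendment 7. The one under Cohort 2 reads "This Cohort will include subjects enrolled under Amendment 7 and later". Subjects are "considered enrolled in the study at the time the informed consent form is signed", which comes before surgery.

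Section 2.2 takes all eyes with attempted implantation and uses both eyes of a bilateral subject. On late second eyes it says "Second eye surgeries after 6 months of the first surgery are also included", and on scope "The above definition applies to both Cohort 1 and Cohort 2". It then limits reporting: "Unless otherwise specified, analyses described below will be reported only for Cohort 2". The rate in section 5.3.1 is "Total # of reported events/Total # of attempted implants x 1,000".

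**The concern.** Take a subject who consented before Amendment 7, with one SND1T4 lens implanted in July 2020 and the other in August 2020. By implant date the subject fits both cohorts. By the Cohort 2 Note the subject does not enter Cohort 2. Depending on the reading, Cohort 2 receives none of this subject's eyes (enrolment), both (implant date by subject), or only the later one (implant date by eye).

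The primary and secondary endpoints are all rates in Cohort 2, so the uncertainty touches both numerator and denominator. About 6 events are expected at the SAP's example rate, so where a single event is placed would show. The study is single-arm and unmasked, so a choice left open could be made with the events in view. Counting by eye would also put second eyes into Cohort 2 without their first eyes. That would disturb the first-eye and second-eye tables and the second Kaplan-Meier censoring rule in section 5.3.1.

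A smaller point is that the interim rates in section 1.5 stand before the Cohort 2 restriction and name no cohort.

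**Working it through.** **1. Where the two rules differ.** The date of Amendment 7 is not in the SAP; it is assumed here to be near the end of July 2020.

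| Subject | In Cohort 2 by implant date | In Cohort 2 by Note |
|---|---|---|
| Both eyes by July 2020, enrolled before Amendment 7 | no | no |
| One eye by July 2020, one after, enrolled before Amendment 7 | yes (and Cohort 1) | no |
| All implants after July 2020, enrolled before Amendment 7 | yes | no |
| All implants after July 2020, enrolled under Amendment 7 or later | yes | yes |

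The rules part only for subjects who consented before Amendment 7 and had at least one eye done after July 2020.

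**2. What the text supports.** Section 1.2 forms groups of subjects, so counting by eye has no basis there. If Cohort 1 enrolment was complete at Amendment 7, and Cohort 2 holds those enrolled under Amendment 7 and later, every subject falls on one side. The implant dates then describe the two periods.

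**3. How many subjects could straddle.** Section 1.2 allows up to 11 scheduled visits: 1 Visit 0 + 2 surgeries + 2 × 4 follow-up visits = 11. Visit 0 is therefore held once. Table 12-1 places it at most 40 days before first-eye surgery and at most 60 days before second-eye surgery. A second eye on or after 1 August 2020 needs a Visit 0 no earlier than 2 June. A first eye by 31 July needs a Visit 0 no later than 31 July. On schedule, only subjects screened in those two months can straddle. A first eye in June means a Visit 0 by 30 June and a second eye by 29 August, so a June and September pair would be out of window.

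**4. The SAP's own figure.** Exact interval: lower = Beta⁻¹(0.025; x, n − x + 1), upper = Beta⁻¹(0.975; x + 1, n − x). Section 9 has N = 3,000 and a rate of 2 per 1,000, so x = 6. The interval is 0.73 to 4.35 per 1,000, width 3.61, which agrees with the stated 3.6.

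**5. Effect on the rate.** Assume 50 straddling subjects added to 3,000 other Cohort 2 eyes with 6 events. All figures are per 1,000.

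| Reading | Events/eyes | Rate (95% CI) |
|---|---|---|
| Enrolment | 6/3,000 | 2.00 (0.73 to 4.35) |
| By subject, no event in these eyes | 6/3,100 | 1.94 (0.71 to 4.21) |
| By subject, one event | 7/3,100 | 2.26 (0.91 to 4.65) |
| By eye, event in the later eye | 7/3,050 | 2.30 (0.92 to 4.72) |
| By eye, event in the earlier eye or no event | 6/3,050 | 1.97 (0.72 to 4.28) |

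With one event and 25 or 100 such subjects, the by-subject rate is 7/3,050 = 2.30 or 7/3,200 = 2.19.

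**6. How likely an event is.** At 2 per 1,000, 100 eyes give 100 × 0.002 = 0.2 expected events. Treating eyes as independent, the chance of at least one is 1 − 0.998¹⁰⁰ = 0.18. The chance of two or more is 0.18 − 100 × 0.002 × 0.998⁹⁹ ≈ 0.02. For 50 eyes, the chance of at least one is 1 − 0.998⁵⁰ ≈ 0.10.

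**The case for a change.** The case for a change is that a primary denominator ought to have one reading. The SAP chose to define the cohorts itself, so the overlap is its own and not something left to the protocol. The Cohort 2 Note says whom the cohort will include, without saying that nobody else belongs. If it merely adds to the date rule, the straddling subject still meets both descriptions. Section 2.2 admits second eyes at any interval, so the 60-day window is no absolute bar. Section 2 settles evaluability before a database lock for each cohort, so every subject must be placed in one. One exclusive rule would take a few sentences.

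Much of this stands. The date sentences do overlap, no tie-break is written, and neither the number of straddling subjects nor the date of Amendment 7 is given. The effect would be larger if these eyes held two events: between 8/3,020 = 2.65 and 8/3,200 = 2.50 for 20 to 200 eyes.

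The conclusion does not follow, however. The rule one would write, with cohort set by the amendment at enrolment and both eyes kept together, is what the two Notes already point to. Separate locks also fit exclusive cohorts. Allocation by consent is fixed before surgery, so on that rule events cannot steer it. The disturbance of the eye tables and the censoring rule arises only if eyes are counted separately, which the text does not support. Section 1.5 describes progress reports on the study as a whole, and leaving the cohort unnamed there contradicts nothing.

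**Conclusion.** No change to the plan follows. The implant-date descriptions in section 1.2 are loosely worded, but the Notes beside them give a workable split by subject. An analyst who follows them obtains a sound Cohort 2 rate.

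The numerical stake is small: 1.94 to 2.00 per 1,000 for an assumed 50 straddling subjects without an event, and about 0.3 per 1,000 if one event is concerned. The intervals overlap almost entirely, and section 5.2 sets no hypothesis, so no conclusion can turn on it.

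This rests on three assumptions: that Amendment 7 took effect near the end of July 2020, that second eyes mostly kept to the Table 12-1 window, and that straddling subjects number in the tens. A much larger number, or several events among them, would make the allocation more visible in the rate, but the Notes would still give the rule.

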#### 2.3 Pharmacokinetic Analysis Set

Not applicable.

# 3 SUBJECT CHARACTERISTICS AND STUDY CONDUCT SUMMARIES

Summary statistics will be provided for demographic characteristics. Number and percentage will be presented for categorical variables and descriptive statistics including mean, standard deviation, median, minimum and maximum will be presented for continuous variables.

#### 4 EFFICACY ANALYSIS STRATEGY

Not applicable. This is a post-approval safety study of the ACRYSOF IQ RESTOR Toric IOL.

#### 5 SAFETY ANALYSIS STRATEGY

# 5.1 Safety Endpoints

The primary safety endpoint is the rate (per 1,000 IOL implants) of post-surgical intraocular inflammation (based upon the specified case definition) reported within a 180-day post-surgical period following attempted implantation of study IOLs for Cohort 2.

The secondary safety endpoints are the rates (per 1,000 IOL implants) of Toxic Anterior Segment Syndrome (TASS), acute postoperative endophthalmitis, chronic postoperative endophthalmitis, and uncategorized cases of post-surgical intraocular inflammation (based

upon the specified case definition), respectively, reported within a 180-day post-surgical period following attempted implantation of study IOLs for Cohort 2.

Other safety endpoints for Cohort 2 are:

- Adverse events
- Device deficiencies
- Problems during surgery
- Other surgical procedures during surgery
- Best Corrected Distance Visual Acuity (BCDVA)
- Intraocular Pressure (IOP)
- Slit lamp observations that include, but not limited to:
  - o Hypopyon
  - Corneal precipitates granulomatous
  - o Corneal precipitates non-granulomatous
  - o Fibrin in the anterior chamber, on the surface of the iris or on the IOL
- Fundus observations
- Slit lamp examinations
  - o Aqueous cell
  - Aqueous flare
  - Eyelid edema
  - Conjunctival hyperemia
  - Ciliary flush
- Corneal Assessment
  - Corneal edema

- Corneal haze
- Evaluation of vitreous cells
- Evaluation of vitreous haze
- Culture of ocular media
- Subject Reported Symptoms

# 5.2 Safety Hypotheses

There are no formal safety hypotheses in this study. The focus of the safety analysis will be a comprehensive descriptive assessment of all safety endpoints stated in Section 5.1.

# **5.3** Statistical Methods for Safety Analyses

Except otherwise stated, the primary analysis set for all safety analyses is the safety analysis set as defined in Section 2.2. The modified safety set will be used for a sensitivity analysis of the primary and secondary safety endpoints. Baseline will be defined as the last measurement prior to exposure to investigational product, except otherwise stated.

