# **5.3.8** Slit Lamp Observations

For each slit-lamp parameter, number and percentages of eyes that experience an abnormality will be presented by overall, first eyes, and second eyes by scheduled visit. A listing will be provided which presents all eyes with an abnormality in any slit-lamp parameter at any postoperative visit.

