# 5.3.10 Slit Lamp Examination

The number and percentage of "worst case" grading for aqueous cell, aqueous flare, eyelid edema, conjunctival hyperemia, and ciliary flush at any postoperative visit will be presented by overall, first eyes, and second eyes. A listing of eyes with a grade for aqueous cells greater than the lowest level, or with a grade for the other type of examination greater than the second lowest level at any postoperative visit will be provided.

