#### 5.3.11.2 Corneal Haze

The number and percentage of "worst case" by grading for corneal haze at scheduled postoperative visits will be presented by overall, first eyes, and second eyes. A listing of eyes with a rating greater than the lowest level (Rating 0 – clear cornea) at any visit will be provided.

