#### **5.3.12 Vitreous Cells**

For eyes with inflammation, the number and percentage of "worst case" evaluation category for vitreous cells at any postoperative visit will be presented by overall, first eyes, and second eyes. A listing of eyes with an evaluation category greater than the lowest level (0 – none; no cells) at any postoperative visit will be provided along with the location and descriptions of vitreous cells.

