# 12 APPENDIX

 Table 12-1
 Schedule of Study Procedures and Assessments

Procedure/ Assessment	Visit 0 (≤ 40 days pre-surgery 1st eye, ≤ 60 days pre-surgery 2nd eye)	Visit 00 & Visit 00A (surgery)	Visit 1 & Visit 1A (Day 1-2 post surgery)	Visit 2 & Visit 2A (Day 7-14 post surgery)	Visit 3 & Visit 3A (Day 30- 60 post surgery)	Visit 4 & Visit 4A (Day 90 - 180 post surgery)	UNSV
Informed Consent	X						
Demographics	X						
Patient Medical History (Ocular and Nonocular) 	X						
Medications (use of medication prior to, during and post-surgery must be documented) 	X	X	X	X	X	X	X
Inclusion/ Exclusion	X	X					
Adverse Events (Volunteered and Elicited)	X	X	X	X	X	X	X
Device Deficiencies		X	X	X	X	X	X
Subject Reported Symptoms	X		X	X	X	X	X
Best Corrected Visual Acuity (BCVA)	X		X	X	X	X	X
Intraocular Pressure	X		X	X	X	X	X
Problems during surgery		X					
Other Surgical Procedures		X					
Aqueous cell	X		X	X	X	X	X
Aqueous flare	X		X	X	X	X	X
Corneal edema	X		X	X	X	X	X
Corneal haze	X		X	X	X	X	X

Fibrin in the anterior chamber, on the surface of the iris or on the intraocular lens (IOL)	X	X	X	X	X	X
Eyelid edema	X	X	X	X	X	X
Conjunctival hyperemia	X	X	X	X	X	X
Ciliary flush	X	X	X	X	X	X
Corneal precipitates	X	X	X	X	X	X
Hypopyon	X	X	X	X	X	X
Dilated fundus examination	X	X 				
Vitreous cell	X	$X^1$	$X^1$	$X^1$	$X^1$	$X^1$
Vitreous haze	X	X 	X 	X 	X 	X1
Photo documentation		$X^2$	X 	$X^2$	$X^2$	X 
Culture of ocular media		$X^2$	$X^2$	$X^2$	$X^2$	$X^2$

 Required for cases of exacerbated post-surgical intraocular inflammation only.

- Medical History: All ocular history, targeted systemic history
- Concomitant Medications: All ocular medications, targeted systemic medications

*NOTE*: Visits with an "A" refer to visits for the 2nd eye visits for cases where both eyes of a subject are enrolled. In the eCRF these visits will be noted with wording of "2nd Eye" instead of A. For example: Visit 1A will be shown as Visit 1-2nd Eye.

 Required at certain visits for cases of exacerbated post-surgical intraocular inflammation. See Manual of Procedures for details on requirements for which visit(s) testing is required.

 Concomitant medications and medical history must be fully documented in the subject source documents. CRF data will be Targeted:

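### The tables of inflammation signs do not use the Visit 0 grades, so they cannot separate new or worsened signs from signs already present before surgery

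*SAP*

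**What the plan says.** **Baseline.** Section 5.3 gives a general rule for the safety analyses: "Baseline will be defined as the last measurement prior to exposure to investigational product, except otherwise stated".

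**Data collected.** The first column of Table 12-1 is headed "Visit 0 (≤ 40 days pre-surgery 1st eye, ≤ 60 days pre-surgery 2nd eye". The aqueous cell row reads "Aqueous cell X X X X X X": a mark at Visit 0, at each of the four postoperative visits and at unscheduled visits. Aqueous flare, corneal edema, corneal haze, fibrin, eyelid edema, conjunctival hyperemia, ciliary flush, corneal precipitates and hypopyon are also marked at Visit 0 and after surgery. Vitreous cell and vitreous haze are marked at Visit 0, and after surgery only for cases of exacerbated inflammation.

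**Summaries planned.**
- Section 5.3.8 (slit lamp observations): "number and percentages of eyes that experience an abnormality will be presented by overall, first eyes, and second eyes by scheduled visit".
- Section 5.3.10 (slit lamp examination), worst grade: "eyelid edema, conjunctival hyperemia, and ciliary flush at any postoperative visit will be presented by overall, first eyes, and second eyes". Aqueous cell and flare are in the same table.
- Section 5.3.11.1 (corneal edema): grades by scheduled postoperative visit.
- Section 5.3.11.2 (corneal haze): "corneal haze at scheduled postoperative visits will be presented by overall, first eyes, and second eyes".
- Sections 5.3.12 and 5.3.13 (vitreous cells and haze), in eyes with inflammation; for cells, the worst "evaluation category for vitreous cells at any postoperative visit will be presented by overall, first eyes, and second eyes".

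Sections 5.3.1 and 5.3.11.1 also plan the inflammation rate split by whether corneal edema is present.

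**The concern.** Randomization does not apply and no comparison group is planned. For these signs, the reference that the study already holds is the same eye's grade before surgery. If that grade is left out, a count of eyes with, say, eyelid edema or corneal haze after surgery mixes two groups: eyes in which the sign appeared or worsened, and eyes in which it was there before and did not change. Only the first group says anything about what followed implantation.

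The SAP applies this principle elsewhere. Section 5.3.7 classifies intraocular pressure by change from baseline and lists eyes against their own baseline. Section 5.3.2 defines a treatment-emergent adverse event as one that is new or has worsened. The inflammation signs, which lie closest to the purpose of the study, have neither device. At stake is what a reader can conclude from the supporting sign tables and from the edema split.

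**Working it through.** **1. Is baseline used for any sign?** Comparing each section with Table 12-1:

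| Section | Graded at Visit 0? | Table | What triggers the listing | Within-eye comparison |
|---|---|---|---|---|
| 5.3.7 Intraocular pressure | Yes | Change from baseline | Change of more than 10 mmHg from the same eye's baseline | **Yes** |
| 5.3.8 Slit lamp observations | Yes | Abnormality, by scheduled visit | Abnormality at any postoperative visit | No |
| 5.3.10 Slit lamp examination | Yes | Worst postoperative grade | Postoperative grade above lowest (aqueous cells) or above second lowest (the others) | No |
| 5.3.11.1 Corneal edema | Yes | Grade by postoperative visit | Grade above 0 at any visit; for eyes with inflammation, at any postoperative visit | No |
| 5.3.11.2 Corneal haze | Yes | Worst case at postoperative visits | Rating above 0 at any visit | No |
| 5.3.12 Vitreous cells | Yes | Worst postoperative category, inflammation eyes | Category above lowest at any postoperative visit | No |
| 5.3.13 Vitreous haze | Yes | Worst postoperative category, inflammation eyes | Category above lowest at any postoperative visit | No |

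No sign section asks for change, shift, a new-or-worsened condition or a flag for findings present at Visit 0. The edema split in Sections 5.3.1 and 5.3.11.1 does not separate pre-existing from new edema.

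**2. The plan's own figure.** Section 9 gives a width of 3.6 per 1,000 for the exact two-sided 95% interval at N = 3,000 and an observed rate of 2 per 1,000. With x = 0.002 × 3,000 = 6, the Clopper-Pearson limits are 0.734 and 4.348 per 1,000, a width of 3.61. The figure is reproduced and is not in dispute; it is used only for the number of cases in step 4.

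**3. How much could pre-existing signs contribute?** The SAP gives no prevalence, so both inputs are assumptions. Let b be the share of eyes with the sign at Visit 0 that keep it unchanged, and i the share of the other eyes that develop it.

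Share of eyes in the table: b + (1 − b) × i. Pre-existing share of those counted: b / [b + (1 − b) × i].

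Example, b = 1% and i = 1%: 0.01 + 0.99 × 0.01 = 1.99%, and 0.01 / 0.0199 = 50%.

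| b | Eyes of 3,000 | In table, i = 1% | Pre-existing share | In table, i = 5% | Pre-existing share |
|---|---|---|---|---|---|
| 0.1% | 3 | 1.10% | 9% | 5.10% | 2% |
| 0.5% | 15 | 1.50% | 33% | 5.48% | 9% |
| 1% | 30 | 1.99% | 50% | 5.95% | 17% |
| 2% | 60 | 2.98% | 67% | 6.90% | 29% |
| 5% | 150 | 5.95% | 84% | 9.75% | 51% |

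The contribution runs from negligible to dominant, depending on two quantities that the SAP does not give.

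**4. Vitreous tables.** At 2 per 1,000 there would be 6 cases in 3,000 eyes or 0.002 × 3,300 = 6.6 in 3,300. One eye with a pre-existing finding is then 1/6 = 17% or 1/6.6 = 15% of the table.

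**The case against.** **No headline estimate is at risk.** A reader might infer that the inflammation rate is inflated. The document does not support that: the primary and secondary rates count events that meet a specified case definition not reproduced in the SAP, and nothing shown feeds the sign tables into them. The signs are other safety endpoints in a descriptive study. This stands.

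**The scale cannot be read against the inflammation rate.** It is tempting to divide an assumed 10 to 50 eyes per 1,000 with a persistent sign by the example rate of 2 per 1,000 and speak of 5 to 25 times as many. Those are unlike quantities, and the SAP never compares them. Nor does it say that such signs are common before surgery; eligibility criteria, not shown here, may exclude some of these eyes. This stands.

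**Some displays already help.** The Section 5.3.8 table is by scheduled visit and can include Visit 0; its named signs are hypopyon, precipitates and fibrin, and for hypopyon and fibrin on the lens the effect is probably small. The main edema listing and the haze listing refer to any visit, so they may show a Visit 0 grade. The Section 5.3.10 listing leaves out the lowest positive grade for every sign but aqueous cells. With about six cases, eye-by-eye review matters more than a vitreous percentage. All of this narrows the point. But a Visit 0 column gives a marginal percentage and cannot show which eyes changed, and the Section 5.3.10 threshold applies to the listing, not to the worst-grade table.

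**Adverse event reporting covers part of it.** Signs reported as adverse events fall under the treatment-emergent definition. That definition does not govern the sign tables.

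**The tables claim only postoperative grades.** True: nowhere are they called new-onset counts. The gap is in what they allow a reader to conclude, not in a false label.

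**Conclusion.** The point holds as a limitation of the supporting sign tables and of the corneal edema split. Sections 5.3.10 to 5.3.13, and to a lesser degree 5.3.8, use absolute grades or presence although the Visit 0 grades are scheduled and a baseline is defined. Without a comparison group, new or worsened signs cannot be told apart from unchanged ones.

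Its size is unknown. The 2% to 84% range is illustrative. It rests on assumed prevalence and onset, and on the sign persisting after surgery; an eye whose sign has cleared by the postoperative visits is not miscounted. Pre-existing signs form a clear majority only when new onset is low relative to persistent prevalence; at 5% onset they pass half only at the top assumption. No effect on the primary or secondary inflammation rates has been shown, and none should be inferred. This is a worthwhile, low-cost improvement rather than an error in the main estimate.

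**What to change.** Keep every existing table. In Sections 5.3.10 to 5.3.13, and if convenient 5.3.8, add one of the following per eye, overall and for first and second eyes:
- a shift table of baseline grade by worst postoperative grade; or
- the number and percentage of eyes whose worst postoperative grade is new or worse than the same eye's baseline.

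For corneal edema, do this at eye level with the worst grade, because grading by location changed on 15 November 2021 and a location-level shift is not available throughout. In the edema split of the inflammation rate, separate edema that is new or worse than baseline from edema already present and unchanged.

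Show the Visit 0 grade in all sign listings. State that the edema and haze listings are triggered by postoperative grades, since the reference to any visit also admits an eye whose only finding was before surgery.

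Cost: about a sentence per section and modest extra programming. The Visit 0 grades are already scheduled, so no new data are needed.
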